## 9.3 TREATMENTS

### 9.3.1 Extent of IP Exposure

For the IP (ABP 798, rituximab (US) or rituximab (EU)), summary statistics will be provided for the total number of doses administered, total dose received, total duration of IP exposure, number of subjects with four full infusions and number of subjects with at least one partial infusion (including missed infusion), number of subjects with at least one infusion delay, number of subjects with at least one infusion missed, and number of subjects with at least one infusion interruption by treatment group. An IP administration summary will also be provided by the reported visit for each dosing/infusion instance, with summaries of the number of subjects receiving a full or partial infusion, infusion delay, infusion missed and infusion interruption as well as reasons, and reasons for ending IP by treatment group. The percentages for the IP administration summary will be based on the number of subjects with the given visit. The analysis will be performed using the safety analysis set according to the actual treatment received.

A subject listing of each administered lot number(s) for IP and a listing of unique manufacturing lot numbers used in the study will be provided.

### 9.3.2 Prior and Concomitant Medications

Prior and concomitant medications will be coded by WHO-DD and will be summarized by preferred name and treatment group. The prior medications and concomitant medications will be summarized by treatment groups. The analysis will be performed using the safety analysis set according to the actual treatment received.

The number and percentage of subjects using each medication will be displayed by treatment arm. Subjects taking more than one medication in the same preferred name will be counted once for the number of subjects taking that preferred name.

Sponsor: Amgen Inc.

Statistical Analysis Plan

Protocol No: 20130108

10-December-2018/ Version 2.0

---

## 9.4 DEMOGRAPHIC AND BASELINE CHARACTERISTICS

The following demographics and baseline characteristics will be summarized by treatment for each of the analysis sets defined in [Section 6](#).

- age (in years, at time of signing informed consent) and age category (<65 vs  $\geq 65$ ),
- race,
- sex,
- ethnicity,
- height,
- weight,
- body mass index (BMI),
- BSA,
- geographic region (North America, Eastern Europe, and Western Europe),
- Number of prior biologic use for RA (1 vs.  $>1$ ),
- Number of prior biologic use for RA (1, 2, 3, etc.),
- seropositivity (RF-positive and/or CCP-positive vs. RF-negative and CCP-negative),
- Duration of RA (in years) and duration of RA category (<5,  $\geq 5$  years),
- DAS28-CRP,
- swollen joint count(66 and 28 counts)
- tender joint count, (68 and 28 counts)
- subject's global health assessment,
- investigator's global health assessment,
- subject's assessment of disease-related pain,
- HAQ-DI,
- CRP,
- use of oral corticosteroid at baseline (Yes/No),
- use of non-steroidal anti-inflammatory drug (NSAID) at baseline (Yes/No),
- baseline methotrexate dose.

Medical conditions at screening and the status of the medical condition at randomization (continuing versus resolved) will be summarized by SOC and PT and tabulated by treatment groups ABP 798/ABP 798, rituximab (US)/ABP 798, rituximab

Sponsor: Amgen Inc.

Statistical Analysis Plan

Protocol No: 20130108

10-December-2018/ Version 2.0

(EU)/rituximab (EU) and total. The analysis will be performed using the safety analysis set according to the actual treatment received.

## 9.5 PHARMACOKINETIC ANALYSES

### 9.5.1 Pharmacokinetic Concentrations

Serum rituximab and ABP 798 concentrations will be summarized descriptively by treatment and nominal sampling time point for the PK concentration analysis set. The following descriptive statistics will be calculated at each of the sampling times: arithmetic mean (mean), coefficient of variation (CV), SD, Q1, Q3, Geometric mean, Geometric CV, minimum, median, maximum and the number of measurements. For calculation of summary concentrations, values below the quantifiable limit (BQL) will be set to zero.

In the event that a subject does not receive the full protocol-specified infusion, subsequent PK samples may be considered not evaluable and excluded from the descriptive statistics and mean concentration-time profiles. In addition, if samples are collected with a substantial deviation from nominal time that impacts the presentation of PK data, they will be excluded from the PK concentration vs nominal time profile. The samples excluded from the PK concentration analysis will be determined based on a blinded data review prior to unblinding for the final analysis.

Individual and mean ( $\pm$ SD) serum concentration-time profiles of rituximab and ABP 798 will be presented graphically using nominal time by treatment on a semi-logarithmic and a linear scale.

### 9.5.2 Pharmacokinetic Parameters

PK parameters for ABP 798 and rituximab will be estimated using noncompartmental analysis methods with Phoenix WinNonlin® Version 6.4 or higher (Pharsight Corp., St. Louis, MO).

In the event that a subject does not receive the full protocol-specified infusion, subsequent PK samples may be considered not evaluable and thus certain PK parameters may not be reportable. In addition, if the full protocol-specified dose was given but there was a long dose interruption or unusually long infusion duration that was deemed to impact PK, the PK profile may be considered not evaluable. The subject exclusion from the PK parameter analysis set will be determined based on a blinded data review prior to unblinding for the final analysis. Any such exclusion will be clearly listed in the CSR along with justification for exclusion.

Pharmacokinetic parameters will be listed by subject and summarized descriptively by treatment for the PK parameter analysis set. The following descriptive statistics will be provided: n, arithmetic mean, SD, Q1, Q3, minimum, median and maximum. Only n, median, Q1, Q3, minimum and maximum will be reported for  $t_{max}$ . In addition, geometric mean, and geometric CV will be calculated for  $AUC_{inf}$ ,  $AUC_{0-14\ day}$ ,  $AUC_{0-12\ wk}$ ,  $C_{max}$ ,  $CLST2$ ,  $t_{1/2}$ ,  $\lambda z$ , CL, MRT,  $AUC\%extrap$  and  $AUC_{last}/AUC_{inf}$ .

The serum PK parameters will be estimated from the individual concentration data for all subjects in the PK parameter analysis set. In estimating the PK parameters, BQL values at

Sponsor: Amgen Inc.

Statistical Analysis Plan

Protocol No: 20130108

10-December-2018/ Version 2.0

the beginning of the profile will be set to zero. BQL values that occur after the first quantifiable point will be considered missing. Actual sampling times will be used in all computations.

## PRIMARY STATISTICAL ANALYSIS

The PK similarity will be demonstrated by comparing the 90% CI for the GMR of test (ABP 798)-to-reference (US-licensed rituximab or EU-authorized rituximab) and rituximab [US] to rituximab [EU] for  $AUC_{inf}$  and for  $C_{max}$  following the second infusion of the first dose with the bounds of 0.8 to 1.25. Point estimates and CIs for the GMR will be estimated from an analysis of covariance model using the PK parameter analysis set. For  $AUC_{inf}$  and  $C_{max}$  after second infusion of the first dose, the point estimates and 90% CIs for the GMR for will be estimated using an analysis of covariance model adjusted for weight and geographic region. A sample SAS code for PROC MIXED is displayed below:

CCI

The geometric least square means for each treatment will be presented. The ratios of the geometric means for the comparison of the test treatment to the reference treatment will be obtained by exponentiating the difference of the means on the natural log scale. The CIs will be obtained by exponentiating the CI for the difference between the means on the log scale. Plots of the ratio of geometric means and 90% CI will be displayed.

Additionally, the similarity between PK endpoints of rituximab (US) and rituximab (EU) will be evaluated as well. The GMRs and 90% CIs will be generated for other PK endpoints:  $AUC_{0-14\ day}$ ,  $AUC_{0-12\ wk}$ , and  $C_{max}$  after the first infusion of the first dose by using the same methods as stated above.

## SENSITIVITY ANALYSES

A sensitivity analysis of all PK parameters will be analyzed similarly to the primary statistical analysis using the PP PK parameter analysis set.

In addition, the following sensitivity analyses will be performed on the PK parameter analysis set:

- The point estimates and CIs for the GMR will be estimated using a model similar to the primary statistical analysis model but excluding all covariates.
- The point estimates and CIs for the GMR will be estimated using the primary statistical analysis model for the subgroups of subjects with negative binding ADA status and negative neutralizing ADA status during first dose period.

Sponsor: Amgen Inc.

Statistical Analysis Plan

Protocol No: 20130108

10-December-2018/ Version 2.0

## 9.6 PHARMACODYNAMICS ANALYSES

All pharmacodynamics analyses will be performed using the FAS according to randomized treatment.

### 9.6.1 CD19

The pharmacodynamics similarity will be evaluated descriptively for the difference in percent of subjects with complete CD19+ cell depletion between test (ABP 798) and reference (US-licensed rituximab or EU-authorized rituximab) from day 1 to day 3. Subjects with baseline value less than 20 cell/uL or missing will not be evaluable for CD19+ depletion analyses. The point estimate, the 90% CI and the 95% CI will be provided for rate difference and will be estimated using a generalized linear model (specifically, a log-binomial regression model) with stratification factors as covariates. A sample SAS code for PROC GENMOD is displayed below:

CCI

Note: The contrasts in the estimate statement may need to be changed depending on the order of the treatments.

Descriptive statistics for CD19+ counts as well as change from baseline will be provided at day 2 and day 3.

In addition, for duration of CD19 complete depletion, KM estimates and 90% CIs will be calculated by randomized treatment group for event time quartiles.

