6.2 Rituximab

Rituximab (Rituxan®, MabThera®) is a genetically engineered chimeric murine/human monoclonal immunoglobulin (Ig) G1 kappa antibody directed against the B cell specific CD20 antigen. In RA patients, treatment with rituximab induces depletion of peripheral B lymphocytes, with the majority of patients demonstrating near complete depletion (CD19 counts below the lower limit of quantification, 20 cells/µL) within 2 weeks after receiving the first dose. Most patients showed peripheral B cell depletion for at least 6 months. A small proportion of patients (~4%) had prolonged peripheral B cell depletion lasting more than 3 years after a single course of treatment ([Biogen Idec, 2013](#)).

Total serum Ig levels, IgM, IgG, and IgA were reduced at 6 months with the greatest change observed in IgM. In RA patients during repeated rituximab treatment, 23.3%,

5.5%, and 0.5% of patients experienced decreases in IgM, IgG, and IgA concentrations below the lower limit of normal, respectively, at any time after receiving rituximab. The clinical consequences of decreases in Ig levels in RA patients are unclear ([Biogen Idec, 2013](#)).

Treatment with rituximab in patients with RA is associated with reduction of certain biologic markers of inflammation such as interleukin (IL)-6, CRP, serum amyloid protein (SAA), S100 A8/S100 A9 heterodimer complex (S100 A8/9), anti-cyclic citrullinated peptide (anti-CCP), and rheumatoid factor (RF; [Biogen Idec, 2013](#)).

Rituximab is indicated, in combination with methotrexate (MTX), for the treatment of adult patients with moderately- to severely-active RA who have had an inadequate response to one or more tumor necrosis factor (TNF) antagonist therapies. Rituximab is approved for use in other indications such as non-Hodgkin lymphoma, chronic lymphocytic leukemia, granulomatosis with polyangiitis, and microscopic polyangiitis ([Biogen Idec, 2013](#)).

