12.6.5 Pharmacodynamics

The PD similarity will be evaluated descriptively by calculating the 90% CI of complete CD19+ cell depletion rate difference between test-to-reference. The 95% CI will also be provided. The point estimate and CIs for rate difference will be estimated using a generalized linear model (specifically, a log-binomial regression model) with relevant baseline values and stratification factors as covariates using the FAS.

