## **5.5 PHARMACODYNAMICS**

### **Complete depletion of CD19+ cell count**

Complete depletion of CD19+ cell count at any post-dose time is defined as CD19+ cell counts  $< 20$  cell/uL ( $0.02 \times 10^9$  cell/L). Subjects with missing CD19+ cell count at baseline or subjects with CD19+ cell count  $< 20$  cell/uL at baseline will be excluded from the derivation of complete depletion of CD19+ cell count.

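### SAP 9.6.1 compares pharmacodynamics between arms only through the share of subjects with CD19+ below 20 cells/µL by day 3; the measured counts get no between-arm estimate (minor, cheap to improve)

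*SAP*

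**What the plan says.** Protocol 12.6.5 evaluates pharmacodynamic (PD) similarity descriptively by "calculating the 90% CI of complete CD19+ cell depletion rate difference between test-to-reference", adds a 95% CI, and fits a log-binomial model on the Full Analysis Set with relevant baseline values and the stratification factors as covariates.

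SAP 9.6.1 keeps that comparison: "The pharmacodynamics similarity will be evaluated descriptively for the difference in percent of subjects with complete CD19+ cell depletion between test (ABP 798") and rituximab (US) or rituximab (EU). "The point estimate, the 90% CI and the 95% CI will be provided for rate difference". Its model has the stratification factors only. The baseline values named in the protocol are gone, and SAP section 10 does not list this among the changes from the protocol.

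The threshold is in SAP 5.5: "Complete depletion of CD19+ cell count at any post-dose time is defined as CD19+ cell counts" under 20 cells/µL.

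For the counts themselves, "Descriptive statistics for CD19+ counts as well as change from baseline will be provided at day 2 and day 3". For duration of depletion, which uses the same threshold, "KM estimates and 90% CIs will be calculated by randomized treatment group for event time quartiles"; this is one estimate per arm, with no contrast between arms. Immunoglobulin levels are summarised by treatment and visit (SAP 9.6.2).

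Blood for CD19+ is drawn at baseline, day 2 and day 3 (Protocol 9.2 to 9.4), so the data for a count comparison are already collected.

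**The concern.** The only PD contrast between arms that carries a confidence interval rests on a yes/no cut. A subject who falls to 21 cells/µL is scored the same as one who stays at 200, and the distance from 20 on either side is ignored. The counts could show whether one product lowers B cells less than another in the first days, but the plan gives no estimate of that difference and no measure of its uncertainty.

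What is at stake is the precision of a supporting comparison. A rate difference with a wide interval says little about PD similarity either way, while a ratio of counts from the same samples could say more. How much more depends on the depletion rate and on whether the assay reports values below 20.

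**Working it through.** **Inputs from the documents.** The threshold is 20 cells/µL (SAP 5.5), with about 100 subjects per arm (Protocol 8.1). Protocol 6.2, describing the reference product from its label, speaks of "CD19 counts below the lower limit of quantification, 20" cells/µL, which is the same value as the cut. The trial assay's own limit is not stated. Neither document gives a PD sample size, power, margin, expected day-3 rate or SD, so there is no planned PD figure to reproduce.

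**Assumptions.** The log count is normal with the same SD in each arm. The endpoint is treated as a single count falling below 20. The depletion rate p runs from 50% to 95%.

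**Precision of the planned estimate.** With 100 evaluable per arm, the half-width of the 90% CI for the rate difference is 1.645 × √(2p(1−p)/100). That is 0.116 at p = 0.5, 0.093 at 0.8 and 0.070 at 0.9. It is wider in practice, because subjects with a missing or already low baseline are excluded.

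**Information lost by the cut.** Let z be the normal quantile at p, and φ the normal density at z. Per-subject information about a shift in the mean log count, relative to a fully measured count (= 1), is:

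- cut at 20: φ²/[p(1−p)]
- count left-censored at 20: φ²/p + zφ + (1−p)

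At p = 0.5, φ = 0.399 and z = 0. The cut gives 0.159/0.25 = 0.637. The censored count gives 0.318 + 0 + 0.5 = 0.818. The loss is 1 − 0.637 = 36% against the full count, and 1 − 0.637/0.818 = 22% against the censored count.

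| p | Cut | Censored | Loss vs full count | Loss vs censored count |
|---|---|---|---|---|
| 0.50 | 0.637 | 0.818 | 36% | 22% |
| 0.70 | 0.576 | 0.655 | 42% | 12% |
| 0.80 | 0.490 | 0.534 | 51% | 8% |
| 0.90 | 0.342 | 0.359 | 66% | 5% |
| 0.95 | 0.224 | 0.231 | 78% | 3% |

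**Adding baseline.** Assume a correlation of 0.5 between log baseline and log day-3 count, so the residual SD is √0.75. Replace z by (z − 0.5b)/√0.75, divide the information by 0.75, and average over a standard normal baseline b. For the censored count this gives 1.047, 0.809, 0.642, 0.416 and 0.259 at the five rates.

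Power serves here only as a common scale. Take a shift that the unadjusted cut would detect with 80% power at one-sided 5%, so that 1.645 + 0.842 = 2.486. Power for another analysis is Φ(2.486 × √ratio − 1.645), where the ratio is its information divided by that of the unadjusted cut. At p = 0.5 the ratio is 1.047/0.637 = 1.644, and Φ(3.188 − 1.645) = 94%.

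| p | Unadjusted cut (SAP) | Baseline-adjusted cut | Baseline-adjusted censored count |
|---|---|---|---|
| 0.50 | 80% | 86% | 94% |
| 0.70 | 80% | 85% | 90% |
| 0.80 | 80% | 85% | 89% |
| 0.90 | 80% | 84% | 86% |
| 0.95 | 80% | 83% | 85% |

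The middle column applies the same adjustment to the cut. Between the last two columns, the gain from using the count is about 8 points at p = 0.5, 5 at 0.7, 4 at 0.8, and 1 to 2 at 0.9 and above. The rest comes from baseline adjustment.

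**The case against.** The strongest reply is that nothing rides on this estimate. PD similarity is not among the primary or secondary objectives (Protocol 7; SAP 2). Both documents call the evaluation descriptive, and there is no margin, hypothesis or error rate. This stands. It limits the matter to the precision of a supporting comparison, and the power figures above are a yardstick for precision, not a property of the plan.

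A second reply is that the counts do appear in the report, with mean, SD, median, quartiles and range by arm (SAP 9). A reader could form a crude difference. This is partly right, but such a difference would be unadjusted, and skewed counts with values near an assay limit are poorly served by arithmetic means.

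A third is that complete depletion is the PD endpoint named in the protocol and matches how Protocol 6.2 describes the reference drug's effect. That is a good reason to keep it. It does not rule out a second estimate.

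A reader might infer that the cut throws away 36% to 66% of the information as a matter of fact. The documents do not support that: the range needs counts to be quantifiable below 20, and the only limit they mention is 20 itself. A reader might also take the early depletion comparison to be the trial's formal test of B-cell effect before it saturates. Nothing is formally tested, and no day-2 or day-3 saturation data are given.

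**Conclusion.** The gap is real and minor. The measured day-2 and day-3 counts have no planned between-arm estimate, and the only PD contrast uses the cut at 20 cells/µL.

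The size is conditional on log-normal counts. For depletion of 50% to 90%, the loss is about 36% to 66% if counts are quantifiable below 20, and about 22% falling to 5% if they are censored there. The assay limit decides which range applies, and the documents do not give it.

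With an assumed baseline correlation of 0.5, replacing the SAP's unadjusted cut by a censored, baseline-adjusted count moves 80% power to about 94% at 50% depletion, 89% at 80%, 86% at 90% and 85% at 95%. Part of that is baseline adjustment, which Protocol 12.6.5 already calls for (without saying which baseline values) and SAP 9.6.1 omits. The primary PK conclusions, the efficacy conclusions and the error rates do not change.

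**What to change.** Keep the depletion percentage as the protocol-named endpoint. Add to SAP 9.6.1, before unblinding, a supportive and descriptive comparison of log CD19+ count at day 2 and at day 3:

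- an ANCOVA-type model with treatment, log baseline count and the stratification factors;
- geometric mean ratios with 90% and 95% CIs for ABP 798 vs rituximab (US) and ABP 798 vs rituximab (EU);
- the CD19 assay limit stated, with counts below it treated as left-censored.

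The SAP has rules for PK concentrations below the limit and for undetectable CRP but none for CD19, so the planned count summaries need such a rule in any case. At the same time, either restore baseline values to the log-binomial model or list their omission in SAP section 10.

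The cost is one extra model and one table on data already collected. The gain is small if nearly all subjects are depleted by day 3 and the assay limit equals the cut; the day-2 comparison may then be the more useful of the two.

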9.10 Week 12 (± 2 days)

Twelve weeks (± 2 days) after the first infusion, the subject will return to the study site for safety and efficacy assessment. The following assessments/procedures will be performed at week 12:

- subjective assessments (Subject's Global Health Assessment, subject's assessment of pain, and HAQ-DI, [Section 17.4](#)); subjective assessments will be the first assessments performed at the visit
- joint assessments (DAS and ACR tender/swollen joint counts; [Section 17.3](#))
- Investigator's Global Health Assessment
- clinical laboratory testing including CRP
- collection of PK samples

Any changes in concomitant medications since the last assessment will be recorded. All AEs, including increases in severity or frequency of pre-existing conditions, will be recorded in the eCRF. SAEs will be reported as outlined in [Section 11.2.2](#).

9.11 Week 24

Twenty-four weeks after the first infusion (or at the time of retreatment if required before week 24), the subject will return to the study site for assessment and treatment. The following assessments/procedures will be performed before treatment at week 24:

- subjective assessments (Subject's Global Health Assessment, subject's assessment of pain, and HAQ-DI; [Section 17.4](#)); subjective assessments will be the first assessments performed at the visit
- physical examination, including evaluation of body systems
- vital signs (systolic and diastolic blood pressure, pulse, respiration rate, and temperature)
- joint assessments (DAS and ACR tender/swollen joint counts; [Section 17.3](#))
- Investigator's Global Health Assessment
- clinical laboratory testing, including serum chemistry, hematology, and CRP
- urinalysis and urine pregnancy test (for women of childbearing potential)
- collection of pretreatment PK samples (within 1 hour predose) and samples for antidrug antibodies, CD19+ cell count, and IgA, IgG, and IgM levels

Any changes in concomitant medications since the last assessment will be recorded. All AEs, including increases in severity or frequency of pre-existing conditions, will be recorded in the eCRF. SAEs will be reported as outlined in [Section 11.2.2](#).

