### 4.3 PREDETERMINED COVARIATES AND PROGNOSTIC FACTORS

For the PK analyses, geographic region and weight will be used as covariates in the model for the primary statistical analysis. The following covariates may be used for further exploration in subgroups:

- Negative binding anti-drug antibodies (ADA) during first dose period
- Negative neutralizing ADA during first dose period

For efficacy analyses, unless stated otherwise, the following stratification factors will be included as covariates in the model or be used to examine treatment effect in subgroups:

- Geographic region (North America vs. Eastern Europe vs. Western Europe)

Sponsor: Amgen Inc.

Statistical Analysis Plan

Protocol No: 20130108

10-December-2018/ Version 2.0

---

- Seropositivity (RF-positive and/or CCP-positive vs. RF-negative and CCP-negative)
- Prior biologic use for RA (1 vs >1)

In case the analysis model doesn't converge, the strata with least number of subjects may be combined to address the convergence issues.

In addition, the following covariates may be used for further exploration in subgroups or as covariates:

- Age Group (<65 years vs  $\geq$ 65 years)
- Race (Caucasian vs Non-Caucasian)
- Gender
- Binding ADA status during first dose period (negative vs positive)
- Neutralizing ADA status during first dose period (negative vs positive)
- Oral Corticosteroid use at baseline (Yes vs No)

Additional baseline demographic and disease characteristics in [Section 9.4](#) may also be considered as covariates in the model for assessing DAS28-CRP change from baseline at week 24.

Analyses that are intended to evaluate the treatment effect and include stratification variables as covariates in the model will be based on the eCRF stratification values, regardless of the subject's IXRS stratification values, to provide unbiased estimates of the effects of treatment and stratification variables without loss of efficiency ([Ke et al, 2017](#)).

For subgroup analyses where the subgroup factor is a stratification variable, an analysis similar to the primary statistical analysis (except the inclusion of the subgroup factor) should be done for each subgroup defined by the eCRF values of the subgroup factor.

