### **Duration of CD19+ B-cell complete depletion**

This variable will be defined only for subjects who had a CD19+ B-cell complete depletion for at least one post-dose time. It is defined as time from the first incidence of complete depletion of CD19+ cell count to when CD 19+ cell count first increases to  $\geq 20$  cell/uL. Subjects whose CD 19+ cell count doesn't increase to  $\geq 20$  cell/uL will be censored at the last CD19 assessment date.

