### 9.7.2 ACR 20/50/70

The analyses of ACR20/50/70 are descriptive. The RR of ACR20/50/70 at week 8, week 12 and week 24 (refers to the analysis visit) will be analyzed based on the day 1 through week 24 time period using a repeated measures analysis, where data are included as observed for both FAS and PP, unless otherwise specified. Besides stratification variables, visit week (as a categorical variable), treatment, and treatment-by-visit interaction will be included in the generalized estimating equation (GEE) model assuming a log link and an AR (1) correlation structure. Both 90% CI and 95% CI will be provided.

A sample SAS code for PROC GENMOD with the repeated statement is displayed below:

CCI

Sponsor: Amgen Inc.

Statistical Analysis Plan

Protocol No: 20130108

10-December-2018/ Version 2.0

CCI

Note: The contrasts in the estimate statement may need to be changed depending on the order of the treatments. Only the individual arm comparison SAS code is presented.

The risk difference (RD) of ACR20 at week 8, week 12 and week 24 between ABP 798 and rituximab arms and corresponding 90% and 95% CIs will be displayed based on a GEE model similar to the above model with the link function changed to 'link=identity' and without the exponential transformation option under LSMESTIMATE and LSMEANS statement.

From Day 1 to EOS, the RR of ACR20/50/70 between ABP 798 and rituximab arms and their corresponding CIs will be estimated at each visit (weeks 8, 12, 24, 40 and 48) using generalized linear model (specifically, a log-binomial regression model) adjusted for the stratification factors as covariates with observed data. A sample SAS code for PROC GENMOD is displayed below:

CCI

Note: The contrasts in the estimate statement may need to be changed depending on the order of the treatments. Only the individual arm comparison SAS code is presented.

The RD of ACR20 between ABP and rituximab arms and their corresponding CIs will be obtained, based on a similar generalized linear model with link function changed to 'link=identity' and without the exponential transformation option under LSMESTIMATE and LSMEANS statements.

The adjusted percent of subjects achieving ACR20/50/70 will be plotted by treatment and week for the FAS accordingly.

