## 10. CHANGE FROM PROTOCOL SPECIFIED ANALYSIS

During the development of this document, pharmacokinetic concentration analysis set was defined in the SAP to better describe the analysis population criteria which will be the population set in the PK serum concentration TFLs. Additionally, the definition of per protocol and per protocol pharmacokinetic parameter analysis sets were modified to include “important protocol deviation” instead of “protocol deviation” to properly reflect the population included in this analysis set.

Sponsor: Amgen Inc.

Statistical Analysis Plan

Protocol No: 20130108

10-December-2018/ Version 2.0

---

Furthermore, per protocol analysis set criteria also includes the condition of 2 full infusion of the first dose, meaning that the drug compliance of 90%-110% of the first dose, additionally to ensure this analysis set follows the protocol requirements.

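### CD19+ depletion: the rate difference is assigned to a log-binomial model with no stated conversion, the protocol's baseline covariate is dropped without record, and duration runs through the second dose

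*SAP*

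**What the plan says.** **Rate difference.** Protocol 12.6.5 asks for a CI for the difference in complete CD19+ depletion rate, from a log-binomial model fitted "with relevant baseline values and stratification factors as covariates using the FAS". SAP 9.6.1 keeps the difference and the model: the estimate and CIs "will be provided for rate difference and will be estimated using a generalized linear model (specifically, a log-binomial regression model". Its covariates are the stratification factors only. Sample GENMOD code is announced, but it is redacted in the public copy. Both documents call the comparison descriptive.

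**The same phrase elsewhere.** For the ACR risk ratio by visit, SAP 9.7.2 uses a "generalized linear model (specifically, a log-binomial regression model) adjusted for the stratification factors as covariates with observed data". For the ACR20 risk difference it says that the estimate is "based on a similar generalized linear model with link function changed to 'link=identity".

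**Record of changes.** SAP section 10 lists three changes, all to analysis sets: a new PK concentration set, the wording of the per-protocol sets ("the definition of per protocol and per protocol pharmacokinetic parameter analysis sets were modified to include" important deviations), and a two-full-infusions condition.

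**Duration.** SAP 5.5 measures depletion from its first occurrence to the first return to 20 cells/uL or more. Subjects who do not return "will be censored at the last CD19 assessment date". SAP 9.6.1 reports Kaplan-Meier quartiles by randomized arm. Protocol 9.11 places the week 24 CD19+ sample ahead of the infusion ("The following assessments/procedures will be performed before treatment at week 24") and moves the rituximab (US) arm to ABP 798 at that infusion.

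**The concern.** A log-binomial model has a log link, so exponentiating its treatment coefficient gives a risk ratio. The plan wants a difference in percentages. A difference can be obtained from such a fit, but only through a further step, such as standardising predicted probabilities over subjects, with its own CI method. The readable text states no such step. A colleague working from the text alone would not know which model produces the reported PD estimate.

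The covariate matters because the protocol lists it and the SAP omits it without record. Duration matters because, after the second infusion course begins, a summary by randomized arm no longer describes the first course of the randomized product.

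**Working it through.** The documents give no depletion rate at day 3, margin or power for this endpoint, so there is no planned figure to reproduce. The check is mainly a comparison of texts, with illustrations of size.

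**1. Scale and model.** With a log link, exp(β) = RR, and RD = p₀(RR − 1), which depends on the reference rate p₀. A constant RR of 0.95 implies:
- p₀ = 0.50: RD = 0.50 × (−0.05) = −0.025
- p₀ = 0.95: RD = 0.95 × (−0.05) = −0.0475

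So the coefficient alone does not give the difference. SAP 9.7.2 treats log-binomial as the ratio model and changes the link for the difference. SAP 9.6.1 has no matching sentence.

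**2. Size of the scale difference.** Assumed rates, n = 100 per arm (the planned number; evaluable subjects may be fewer), unadjusted, 90% Wald CI, z = 1.645. SE(ln RR) = √[(1−p₁)/(n p₁) + (1−p₀)/(n p₀)]; SE(RD) = √[p₁(1−p₁)/n + p₀(1−p₀)/n].

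| Test vs reference | RR (90% CI) | RD (90% CI) |
|---|---|---|
| 95% vs 90% | 1.056 (0.988 to 1.128) | 0.050 (−0.011 to 0.111) |
| 60% vs 50% | 1.200 (0.970 to 1.484) | 0.100 (−0.015 to 0.215) |

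First row: SE(ln RR) = √(0.05/95 + 0.10/90) = 0.0405; SE(RD) = √(0.000475 + 0.0009) = 0.0371. These rows compare two scales on the same data. They do not measure an error in the plan.

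**3. How candidate models behave.** Simulation with 3 × 100 subjects, an assumed region mix of 20/60/20, 80% seropositive, 50% with one prior biologic, and no treatment or covariate effects. Boundary means that the constrained maximum-likelihood fit puts a cell probability at 0 or 1 (1,000 runs per rate; every run converged). The logistic results use 5,000 runs and a delta-method 90% CI.

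| Depletion rate | 60% | 80% | 90% | 95% |
|---|---|---|---|---|
| Identity link, on boundary | 0% | 11% | 51% | 92% |
| Log link, on boundary | 0.9% | 17% | 58% | 94% |
| Logistic standardised RD, coverage | 88.9% | 89.6% | 89.1% | 89.6% |
| Logistic fit, separation | 0% | 0% | 0.8% | 15% |
| Unadjusted RD, Newcombe 90% CI, coverage | 89.9% | 90.1% | 89.7% | 90.9% |

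At a 98% rate, separation reaches 72%. SAP 4.3 says that "the strata with least number of subjects may be combined to address the convergence issues"; it says so after the efficacy covariates, so its use for PD is an assumption. Removing region altogether still leaves 18% (identity) and 22% (log) of fits on the boundary at 90%, and 61% and 64% at 95%.

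**4. Baseline covariate.** Assuming an effect of 1 log-odds per SD, including it narrows the mean CI width by 9/7/5/3% at rates of 60/80/90/95%.

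**5. Duration.** Scheduled post-dose CD19+ samples are days 2 and 3 and weeks 4, 24 and 48 (Protocol 9.3, 9.4, 9.8, 9.11, 9.15). Four precede the second dose and one follows it. Take a subject first depleted on day 2, with the SAP 5.1 target days:
- recovered at the week 24 sample: event at 169 − 2 = 167 days, before the second dose;
- still depleted at week 24 and re-dosed: event or censoring at 337 − 2 = 335 days, after the second course;
- the same subject, if censored at the second dose: 167 days.

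Protocol 6.2 says that most patients stay depleted for at least six months, so the second path should be common.

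**The case against.** The strongest reply is that the link and estimate statements sit in the redacted code, and redacted text is not missing from the plan. The target quantity is clear and agrees in both documents, and SAP 9.7.2 shows that the authors know to use an identity link for a difference. The hidden code may do so, or may convert from the ratio. This stands. A reader might infer that a risk ratio will be reported as a rate difference, but the documents do not support that. They show only that the readable text names a ratio model and states no conversion.

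A reader might also infer that a logistic model is the only sound replacement. That is not supported either: the SAP's own identity-link method answers the wording problem. The simulation rests on assumed rates and strata, its constrained fit is not GENMOD, and it gives no bias or coverage for the identity-link difference.

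On the covariate, the protocol does not name its baseline values, and Protocol 12.3 leaves detail to the SAP. Baseline CD19+ count is the natural reading, but it is an inference. The SAP does use that count to decide who is evaluable, which is not adjustment. The omission from section 10 remains.

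On duration, only quartiles per arm are planned, with no test between arms, and SAP 9.7 has an efficacy period that runs past the second dose as well as one that stops there. This shows that the current analysis has a use, but not that it isolates the first course.

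**Conclusion.** The point holds at minor severity, in three parts.

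1. Protocol 12.6.5 and the readable text of SAP 9.6.1 attribute a rate difference to a log-binomial model without an identity link or conversion step. No wrong reported number can be shown.
2. SAP 9.6.1 drops the protocol's baseline covariates and section 10 does not say so. This does not depend on how the redacted code sets the link. The precision at stake is 3 to 9% of CI width, under an assumed covariate effect.
3. Under the SAP 5.5 censoring rule, depletion duration by randomized arm mixes two courses, and in the rituximab (US) arm two products, for subjects still depleted at week 24 who are re-dosed.

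The comparison carries no margin or alpha, so the PK and DAS28-CRP conclusions are untouched. All depletion rates used here are assumptions.

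**What to change.** - **SAP 9.6.1, model.** Name a model for the risk difference and make text and code agree. Either an identity-link binomial model as in 9.7.2, or a difference standardised from a logistic or log-binomial fit, would do. State the CI method (for a standardised difference, delta method or bootstrap) and a fallback, such as the unadjusted difference with a Newcombe CI, for a failed fit or an arm that is 100% depleted. If rates near or above 90% are expected, the simulation favours the standardised logistic difference.
- **SAP 9.6.1, covariate.** Restore baseline CD19+ count, which is already collected, or record its removal in section 10. Record any change from the protocol's model there too.
- **Duration.** Add an analysis censored at the first infusion of the second dose and keep the current one as supportive. The price is that the median or other quartiles may not be reached.

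The cost is SAP wording, a few lines of code and section 10 entries, with no new data. Protocol 12.6.5 can stay as it is, since Protocol 15.2 would make any change to it an amendment.
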